10.4.1.4 Events of special interest

An EOSI is a serious or non-serious AE of scientific and medical concern specific to the Sponsor’s product or program, for which ongoing monitoring may be appropriate. Such events may require further investigation in order to characterize and understand them. These events should be reported on the specific eCRF page and will only qualify for expedited reporting when serious (fulfilling SAE criteria).

The EOSI for this study are:

- MACE (CV death, MI, or stroke) and other specific CV events (eg, heart failure leading to hospitalization)
- Severe hypoglycemia (see [Section 9.2.1.2](#))
- Genital mycotic infections (to include vulvovaginal candidiasis in females and candidal balanitis in males)
- UTIs
- Clinically relevant volume depletion and events related/possibly related to volume depletion
- Diarrhea
- Pancreatitis
- Bone fractures
- Venous thrombotic events to include deep venous thrombosis and thromboembolism (to include pulmonary embolism)
- DKA
- Renal events to include 50% decline in eGFR, end stage kidney disease, renal death

- Malignancies of special interest (breast, bladder, renal cell, Leydig cell, pancreatic, prostate, and thyroid carcinoma)
- Adverse events leading to an amputation.

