11.4.3.4 Analysis of events of special interest

The number (%) of patients with each EOSI event will be summarized by treatment group. All events reported by the Investigators on the AE forms for special interest will be listed along with the adjudication outcome (if applicable).

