2.1.4.2 Adverse events variables

Adverse event observation period

- Pretreatment adverse events are adverse events that developed or worsened or became serious from the signed informed consent date up to first administration of double-blind IMP
- Treatment-emergent adverse events are adverse events that developed or worsened or became serious during the treatment-emergent adverse event period
- Posttreatment adverse events are adverse events that developed or worsened or became serious during the posttreatment period.

All adverse events (including SAE, AESI and EOSI) will be coded to a lower-level term (LLT), preferred term (PT), high-level term (HLT), high-level group term (HLGT), and associated primary system organ class (SOC) using the version of MedDRA currently in effect at Covance at the time of database lock.

The occurrence of adverse events (including SAE, AESI and EOSI) will be recorded from the time of signed informed consent until the end of the study (see [Section 2.1.4](#)) or the resolution/stabilization of all SAE, AESI and EOSI.

AE SI include:

- Pregnancy
- Symptomatic overdose with IMP/NIMP
- Alanine aminotransferase (ALT) increase > 3 times upper limit of normal (ULN)

EO SI include:

- MACE (CV death, myocardial infarction, or stroke) and other specific cardiovascular events (eg, heart failure requiring hospitalization)
- Severe hypoglycemia
- Genital mycotic infections (to include vulvovaginal candidiasis in females and candida balanitis in males)
- Urinary tract infection
- Clinically relevant volume depletion and events related/possibly related to volume depletion
- Diarrhea
- Pancreatitis
- Bone fractures
- Venous thrombotic events, to include deep venous thrombosis and thromboembolism (to include pulmonary embolism)
- Diabetic ketoacidosis
- Renal events, to include 50% decline in eGFR, end stage kidney disease, renal death
- Malignancies of special interest (breast, bladder, renal cell, Leydig cell, pancreatic, prostate, and thyroid carcinoma)
- Adverse event leading to an amputation

A Clinical Endpoint Committee(s) (CEC) will in a blinded manner review and adjudicate all deaths, myocardial infarction, stroke, unstable angina requiring hospitalization, and heart failure requiring hospitalization, selected renal events, bone fracture, and diabetic ketoacidosis.

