Two independent committees will review safety events that require ongoing monitoring to ensure timing protocol amendments in case a safety signal is identified. These events are: 1) potential cases of drug-induced liver injury (DILI), and 2) cases of amputations. The two committees will review the cases in a treatment-blinded manner and will present their assessment to the DMC.

AE SI and EO SI will be identified based on criteria in [Table 3](#).

Table 3 - Criteria for AESI and EOSI

AE Grouping	Criteria
AESI	
Pregnancy	eCRF "Pregnancy"
Symptomatic overdose with IMP/NIMP	"Overdose of IMP" or "Overdose of NIMP" checked and "Symptomatic overdose" checked in eCRF "Overdose"
ALT increase > 3X ULN	eCRF "ALT increase"
EOSI adjudicated	
Cardiovascular death	Positively adjudicated by CEC: "Cardiovascular" or "Undetermined" as the primary cause of death
Myocardial infarction, Unstable Angina requiring hospitalization	Positively adjudicated by CEC: Yes to the question "Does the event meet the definition of an MI for this study?", or Yes to the question "If event is not an MI, does the event meet the definition of an UA Requiring admission to hospital or emergency room, for this study?"
Stroke	Positively adjudicated by CEC: Yes to the question "Does the event meet the definition of a Stroke for this study?"
Heart failure requiring hospitalization	Positively adjudicated by CEC: Yes to the question "Does the event meet the definition of a Heart Failure Event for this study?"
Bone fractures	Positively adjudicated by CEC: Yes to the question "Did the Fracture occur?"
Diabetic ketoacidosis	Positively adjudicated by CEC: Yes to the question "Does this event meet the criteria to be a DKA event?"
EOSI Renal events where select events adjudicated	
Sustained $\geq 50\%$ decrease in eGFR	(1) For $\geq 50\%$ decrease in eGFR from baseline, (1a) confirmed $\geq 50\%$ decrease in GFR for ≥ 30 days with no reversible cause as recorded in eCRF "eGFR decrease", OR (1b) positively adjudicated by CEC: Yes to the question "Does the subject meet the criteria of CKD progression" for $\geq 50\%$ decrease in eGFR.
Sustained eGFR < 15 mL/min/1.73 m ²	(2) For eGFR < 15 mL/min/1.73 m ² , (2a) confirmed eGFR < 15 mL/min/1.73 m ² for ≥ 30 days with no reversible cause as recorded in eCRF form "eGFR decrease", OR (2b) positively adjudicated by CEC: Yes to the question "Does the subject meet the criteria of CKD progression".

Statistical Analysis Plan

Version: Final 2.0

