- TEAEs (PTs with an incidence ≥5% in any treatment group) by primary SOC, HLGT, HLT, and PT, sorted by internationally agreed order of SOCs. The other levels (HLGT, HLT, PT) will be presented in alphabetic order.

Analysis of all treatment emergent serious adverse event(s)

- All treatment-emergent serious adverse events by primary SOC, HLGT, HLT, and PT, showing the number (%) of patients with at least 1 serious treatment-emergent adverse event, sorted by the internationally agreed SOC order. The other levels (HLGT, HLT, PT) will be presented in alphabetical order.
- All treatment-emergent serious adverse events regardless of relationship and related to IMP, by primary SOC, HLGT, HLT, and PT, showing the number (%) of patients with at least 1 treatment-emergent serious adverse event, sorted by the internationally agreed SOC order. The other levels (HLGT, HLT, PT) will be presented in alphabetical order.

Analysis of all treatment-emergent adverse event(s) leading to treatment discontinuation

- All treatment-emergent adverse events leading to treatment discontinuation, by primary SOC, HLGT, HLT, and PT, showing the number (%) of patients sorted by the internationally agreed SOC order. The other levels (HLGT, HLT, PT) will be presented in alphabetical order

Analysis of adverse events of special interest

Pregnancy and overdose will be included in overall AE summaries if any are reported. ALT increase >3 x ULN is included in laboratory PCSA summary if any.

In addition, the number (%) of patients with an AESI will be summarized by PT and by treatment group. Corresponding listings will be provided as appropriately.

Analysis of events of special interest

Cardiovascular events, bone fracture and DKA

For EOSIs that are adjudicated (ie, deaths, myocardial infarction, stroke, and unstable angina requiring hospitalization, heart failure requiring hospitalization, bone fracture, and diabetic ketoacidosis), the number (%) of patients with an EOSI positively adjudicated by CEC will be summarized by treatment group. All EOSIs sent for adjudication and/or reported by the investigators in the specific AE forms will be listed along with the adjudication outcome.

Renal events

For the EOSI renal events where selected events are adjudicated, the number (%) of patients with any renal events identified in [Table 3](#) in [Section 2.1.4.2](#) will be summarized by treatment group.

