The following renal events will be listed along with the adjudication outcome if applicable, including events,

- i. recorded in e-CRF “GFR decrease”,
- ii. recorded in e-CRF “Renal Event – Dialysis”,
- iii. identified as “Renal transplant” in e-CRF “Other procedure”,

Renal death will be part of all deaths specified above.

Other EOSIs

For EOSIs that are not adjudicated, the number (%) of patients with at least one event will be summarized by treatment group and by PT (as identified in [Table 3](#) in [Section 2.1.4.2](#)).

Severe hypoglycemia will be included in the summary of hypoglycemia (See [Section 2.4.5.1](#))

AE leading to an amputation is described in the section below.

Analysis of Amputation

The number (%) of patients with amputation will be summarized by treatment group and by PT during the study (ie, regardless of on- or post-treatment). Amputation is a procedure recorded in eCRF “Other Procedures related to Amputation”. Patients who had a procedure related to amputation will be listed.

The number (%) of patients with an “AE leading to an amputation” will be summarized by treatment group and by PT. The “AE leading to an amputation” is determined by the AE identifier recorded in eCRF “Other Procedures related to Amputation” when “AE correction” is chosen as the reason for the amputation procedure.

In addition, the number (%) of patients with an “AE potentially leading to an amputation” will be summarized by treatment group and by PT (as identified in [Table 3](#) in [Section 2.1.4.2](#)). The associated list will be provided as well, with patients who had an amputation procedure flagged. “AE potentially leading to an amputation” represents the condition that commonly precedes the amputation procedure, but not in all cases an amputation has occurred.

Analysis of pretreatment and posttreatment adverse events

- All pretreatment adverse events by primary SOC and PT, showing the number (%) of patients with at least 1 pretreatment adverse event, sorted by the internationally agreed SOC order and decreasing incidence of PTs within each SOC in the sotagliflozin 400 mg group

- All posttreatment adverse events by primary SOC and PT, showing the number (%) of patients with at least 1 posttreatment adverse event, sorted by the internationally agreed SOC order and decreasing incidence of PTs within each SOC in the sotagliflozin 400 mg group

Listings

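### The SAP's by-arm count of renal events of special interest leaves out non-sustained or reversible 50% falls in eGFR that the protocol's definition includes

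*SAP*

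**What the plan says.** **Definition.** Protocol 10.4.1.4 lists among the events of special interest (EOSI): "Renal events to include 50% decline in eGFR, end stage kidney disease, renal death". SAP 2.1.4.2 repeats this almost word for word: "Renal events, to include 50% decline in eGFR, end stage kidney disease, renal death". Neither sentence sets a minimum duration, a confirmation rule or a condition on cause.

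**Promised analysis.** Protocol 11.4.3.4 states: "The number (%) of patients with each EOSI event will be summarized by treatment group".

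**Planned analysis.** SAP 2.4.5.2 describes the renal summary as "For the EOSI renal events where selected events are adjudicated, the number (%) of patients with any renal events identified in" Table 3. Table 3 (SAP 2.1.4.2) admits an eGFR decrease of 50% or more by either of two routes:
- The decrease is confirmed for at least 30 "days with no reversible cause as recorded in eCRF" (the eGFR decrease form).
- The Clinical Endpoint Committee (CEC) answers yes to "Does the subject meet the criteria of CKD progression".

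**Listing.** SAP 2.4.5.2 continues: "The following renal events will be listed along with the adjudication outcome if applicable, including events", and names the GFR decrease, dialysis and transplant records.

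**The concern.** The counted event is narrower than the defined one. If a patient's eGFR halves and then recovers, or halves from a cause judged reversible, the protocol definition is met. The patient enters the renal count by arm only if the CEC calls the event CKD progression.

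The excluded type of event is not remote in this trial. Protocol 4.5 names volume depletion as a risk and notes small GFR decreases with the SGLT2 inhibitor class. Protocol Appendix C asks for volume status to be assessed in patients with renal impairment, the elderly, and those on diuretics or renin-angiotensin drugs. Exclusion E31 admits patients with eGFR down to 30 mL/min/1.73 m². A reader who takes the renal EOSI table as the count of protocol-defined events could therefore read too low a number for any arm.

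The SAP sentence also speaks of patients with any Table 3 renal event, where the protocol promises each event. It is unclear whether the components will be shown separately.

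**Working it through.** The plan states no figure on this point, so there is none to reproduce. The check has two parts: compare the definitions, then see whether another planned by-arm table supplies the missing count.

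**1. Definitions side by side**

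| | Protocol 10.4.1.4 | SAP Table 3, as counted in 2.4.5.2 |
|---|---|---|
| Size of fall | 50% | at least 50% from baseline |
| Duration | none stated | at least 30 days (first route) |
| Cause | none stated | no reversible cause (first route) |
| Alternative | none | CEC adjudicates CKD progression |

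A fall that fails both SAP routes is an EOSI under the protocol. In the SAP it is listed only.

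**2. Creatinine abnormality (PCSA) rows**

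Inputs: SAP 2.5.1 gives MDRD eGFR proportional to creatinine^(−1.154). SAP Appendix A counts creatinine changes of at least 30% and at least 100% from baseline. SAP 2.4.5.4 counts these by arm at any time in the treatment-emergent period, unscheduled values included, with no persistence rule.

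With age, sex and race fixed:
- 50% eGFR fall: creatinine ratio = 2^(1/1.154) = 1.823, a rise of 82.3%.
- Creatinine +30%: eGFR fall = 1 − 1.3^(−1.154) = 26.1%.
- Creatinine +100%: eGFR fall = 1 − 2^(−1.154) = 55.1%.

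Every on-treatment halving therefore meets the 30% row, but that row also holds falls from about 26%. The 100% row misses falls between 50% and about 55%. The baselines for creatinine and eGFR are each averages of all pre-dose values, so the mapping is approximate for an individual patient. The distance between 82% and 30% leaves the first conclusion safe.

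**3. eGFR category rows**

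SAP Appendix A uses absolute bands, not change from baseline. Halving moves patients as follows:
- Baseline 30 to <60: to 15 to <30. Few patients start below 30, given E31, so this case is fairly visible.
- Baseline 60 to <120: to 30 to <60. For example, 75 becomes 37.5. A patient with a stable value in that band is in the same category.
- Baseline 120 to <180: to 60 to <90. For example, 125 becomes 62.5.

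**4. Adverse event tables**

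Protocol 10.4.2 gives being an EOSI as one example of when a laboratory abnormality is recorded as an AE, subject to the investigator's judgement of medical relevance. A treatment-emergent case so recorded is counted by arm under whatever preferred term it is coded to. SAP Appendix B has no renal-event term list. Its volume depletion list includes prerenal failure, which would catch some cases if they are coded there.

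**Result.** By-arm tables other than the renal one include these patients. None shows the number with an eGFR fall of 50% or more.

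**The case against.** The best case for the SAP is that nothing is hidden and little is lost. SAP Table 2 (section 1.6) declares the detailed renal criteria as a clarification made for consistency with the outcome studies. The protocol names the 50% decline beside end stage kidney disease and renal death, so a sustained reading is a reasonable one. Safety analyses are descriptive, the listing shows every entry on the GFR decrease form, and the tables in the check above give counts by arm. All of this stands, and it is why the point is minor. It does not supply the count promised in Protocol 11.4.3.4.

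Three stronger readings are tempting, and the documents do not support them:
- **That these falls are counted by arm nowhere.** The 30% creatinine row alone rules this out for on-treatment cases.
- **That a fall first seen at Week 52 cannot be confirmed.** The only later scheduled chemistry is at Visit 16, and 378 − 364 = 14 days. However, Protocol 10.4.2 follows AEs until laboratory results normalise or stabilise, beyond the last planned visit if needed, and the SAP's posttreatment epoch (2.1.4) can run to resolution or stabilisation of EOSIs.
- **That acute injury will be the main renal signal and the renal table will read zero.** The protocol speaks of small GFR decreases and gives no rate for falls of 50% or more.

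The CEC's criteria for CKD progression are in a charter outside these documents. How much the second route would recover cannot be judged from here.

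**Conclusion.** The concern holds in limited form. The renal EOSI summary by arm is narrower than the protocol's definition. Non-sustained or reversible halvings that the CEC does not call CKD progression are listed but left out of that summary, and no other planned row isolates them.

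The number affected is unknown. As an illustration only, assume that 0.5% to 2% of patients have such a fall. That would be 1.4 to 5.6 patients among 280 (400 mg) and 0.7 to 2.8 among 140 (200 mg or placebo). The rate is an assumption with no basis in the documents.

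No efficacy result is touched, and by-arm data of a coarser kind are already planned. Severity is minor, and the change is a cheap improvement. The conclusion rests on reading the protocol's wording as unconditional, which is how both documents state it.

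**What to change.** Keep the sustained or adjudicated row, so that the trial stays comparable with the outcome studies. Add to Table 3 and section 2.4.5.2 a separately labelled row: any decrease in eGFR of 50% or more from baseline during the treatment-emergent period, regardless of duration or cause, derived from central-laboratory eGFR. Report it, and each renal component, by treatment group.

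The SAP already does something similar for amputation, where a broader by-arm row stands beside the protocol's event.

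The cost is a few lines of SAP text and one table row from data already collected. The downside is that the row will include some unconfirmed single values, which its label should say.

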Lexicon Pharmaceuticals Protocol No. EFC14868

Date of Issue: 04 December 2019
Covance Study ID:000000155200

AE Grouping	Criteria
Chronic dialysis	(3) For dialysis, (3a) dialysis lasted for ≥90 days (e.g. end date – start date+ 1 ≥90) as recorded in eCRF “Renal Event – Dialysis”, OR (3b) positively adjudicated by CEC: Yes to the question “. Does the subject meet the criteria for ESRD”.
Renal transplant *	(4) “Renal transplant” captured in eCRF “Other procedure form”, where adjudication is not required. PTs of Renal transplant (10038533), Renal and pancreas transplant (10052278), Renal and liver transplant (10052279) based on MedDRA v22.0.
Renal death	(5) Renal death as positively adjudicated by CEC: “Death - Non-Cardiovascular (Renal)” as the primary cause of death

EOSI not adjudicated *

Severe hypoglycemia	algorithm specified in Section 2.1.4.1 based on eCRF “Hypoglycemic Events”
Genital mycotic infections	PTs in Appendix B
Urinary tract infections	PTs in Appendix B
Clinically relevant volume depletion and events related/possibly related to volume depletion	PTs in Appendix B
Diarrhea	Narrow search on “Noninfectious diarrhoea (SMQ)” [20000218] plus the following PTs (MedDRA v22.0): Gastroenteritis (10017888), Antidiarrhoeal supportive care (10055660), Enteritis (10014866), Enteritis leukopenic (10014877), Enterocolitis (10014893), Enterocolitis haemorrhagic (10014896)
Pancreatitis	PTs in Appendix B
Venous thrombotic events	PTs in Appendix B

AE Grouping	Criteria
Malignancies of special interest	
Breast cancer: Narrow search on “Breast cancer: Narrow search on “Breast neoplasms, malignant and unspecified (SMQ)” [20000149]
 
Prostate cancer: Narrow search on “Prostate neoplasms, malignant and unspecified (SMQ)” [20000152]
 
Leydig-cell cancer: PTs of Leydig cell tumour of the testis (10024407) and Ovarian Sertoli-Leydig cell tumour (10073270) based on MedDRA v22.0
 
Thyroid cancer: PTs in Appendix B
 
Renal cell cancer: PTs in Appendix B
 
Pancreatic cancer: PTs in Appendix B
 
Bladder cancer: PTs in Appendix B

EOSI AE leading to an amputation

AE leading to an amputation	“AE Correction” as the reason for amputation in eCRF “Other Procedures related to Amputation”
AE potentially leading to an amputation *	PTs in Appendix B

* Search terms will be updated using the MedDRA version currently in effect at Covance at the time of database lock for EOSI identified by them.

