Appendix B List of PTs for select EOSIs (MedDRA v22.0)

EOSI	Preferred Term Code	Preferred Term
Genital Mycotic Infections	10004074	Balanitis candida
Genital Mycotic Infections	10018143	Genital candidiasis
Genital Mycotic Infections	10047784	Vulvovaginal candidiasis
Genital Mycotic Infections	10061180	Genital infection fungal
Genital Mycotic Infections	10064899	Vulvovaginal mycotic infection
Genital Mycotic Infections	10065582	Urogenital infection fungal
Genital Mycotic Infections	10071209	Candida cervicitis
Genital Mycotic Infections	10079521	Fungal balanitis
Urinary tract infections	10011781	Cystitis
Urinary tract infections	10011790	Cystitis escherichia
Urinary tract infections	10011797	Cystitis klebsiella
Urinary tract infections	10011799	Cystitis pseudomonal
Urinary tract infections	10017525	Fungal cystitis
Urinary tract infections	10018185	Genitourinary chlamydia infection
Urinary tract infections	10023424	Kidney infection
Urinary tract infections	10037584	Pyelitis
Urinary tract infections	10037596	Pyelonephritis
Urinary tract infections	10037597	Pyelonephritis acute
Urinary tract infections	10037601	Pyelonephritis chronic
Urinary tract infections	10037603	Pyelonephritis mycoplasmal
Urinary tract infections	10037653	Pyonephrosis
Urinary tract infections	10038351	Renal abscess
Urinary tract infections	10044828	Tuberculosis of genitourinary system
Urinary tract infections	10046424	Urethral abscess
Urinary tract infections	10046480	Urethritis
Urinary tract infections	10046482	Urethritis chlamydial
Urinary tract infections	10046483	Urethritis gonococcal
Urinary tract infections	10046490	Urethritis ureaplasma
Urinary tract infections	10046571	Urinary tract infection
Urinary tract infections	10046572	Urinary tract infection enterococcal
Urinary tract infections	10046704	Urogenital trichomoniasis
Urinary tract infections	10048302	Tubulointerstitial nephritis
Urinary tract infections	10048709	Urosepsis
Urinary tract infections	10048837	Cystitis glandularis
Urinary tract infections	10049059	Urinary tract infection fungal
Urinary tract infections	10049100	Pyelocystitis
Urinary tract infections	10051250	Ureteritis
Urinary tract infections	10051350	Cytomegalovirus urinary tract infection
Urinary tract infections	10051959	Urinary bladder abscess
Urinary tract infections	10052238	Escherichia urinary tract infection

Statistical Analysis Plan

Version: Final 2.0

Lexicon Pharmaceuticals Protocol No. EFC14868

Date of Issue: 04 December 2019

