Covance Study ID:000000155200

Urinary tract infections	10054088	Urinary tract infection bacterial
Urinary tract infections	10056351	Emphysematous cystitis
Urinary tract infections	10058523	Bladder candidiasis
Urinary tract infections	10058596	Renal cyst infection
Urinary tract infections	10059517	Bacterial pyelonephritis
Urinary tract infections	10061181	Genitourinary tract gonococcal infection
Urinary tract infections	10061182	Genitourinary tract infection
Urinary tract infections	10061395	Ureter abscess
Urinary tract infections	10062279	Urinary tract infection pseudomonal
Urinary tract infections	10062280	Urinary tract infection staphylococcal
Urinary tract infections	10064825	Urinary tract infection viral
Urinary tract infections	10064921	Urinary tract inflammation
Urinary tract infections	10065197	Cystitis viral
Urinary tract infections	10065198	Cystitis bacterial
Urinary tract infections	10065199	Cystitis helminthic
Urinary tract infections	10065213	Pyelonephritis viral
Urinary tract infections	10065214	Pyelonephritis fungal
Urinary tract infections	10065582	Urogenital infection fungal
Urinary tract infections	10065583	Urogenital infection bacterial
Urinary tract infections	10066757	Urinary tract abscess
Urinary tract infections	10068822	Emphysematous pyelonephritis
Urinary tract infections	10070300	Streptococcal urinary tract infection
Urinary tract infections	10074409	Escherichia pyelonephritis
Urinary tract infections	10075063	Urethritis mycoplasmal
Urinary tract infections	10078665	Bacterial urethritis
Urinary tract infections	10081163	Fungal urethritis
Urinary tract infections	10081262	Candida urethritis
Urinary tract infections	10082040	Nephritis bacterial
Volume depletion	10005697	Blood osmolarity increased
Volume depletion	10005731	Blood pressure ambulatory decreased
Volume depletion	10005734	Blood pressure decreased
Volume depletion	10005737	Blood pressure diastolic decreased
Volume depletion	10005748	Blood pressure immeasurable
Volume depletion	10005758	Blood pressure systolic decreased
Volume depletion	10005761	Blood pressure systolic inspiratory decreased
Volume depletion	10007979	Central venous pressure decreased
Volume depletion	10009192	Circulatory collapse
Volume depletion	10012174	Dehydration
Volume depletion	10013578	Dizziness postural
Volume depletion	10021097	Hypotension
Volume depletion	10021137	Hypovolaemia
Volume depletion	10021138	Hypovolaemic shock
Volume depletion	10026983	Mean arterial pressure decreased

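### The genital mycotic infection count rests only on eight preferred terms that all name a fungal cause, so an investigator-reported event coded without one is left out of that count

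*SAP*

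**What the plan says.** **Protocol.** Section 10.4.1.4 makes genital mycotic infection an EOSI, with candidal infection in women and in men as the named examples. Of EOSIs in general it says "These events should be reported on the specific eCRF page". Section 11.4.3.4 then says "The number (%) of patients with each EOSI event will be summarized by treatment group", and adds that every event investigators enter on the special-interest AE forms will be listed, with the adjudication result where there is one.

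**SAP.** Section 2.4.5.2, under Other EOSIs, says "For EOSIs that are not adjudicated, the number (%) of patients with at least one event will be summarized by treatment group", with a breakdown by PT, and points to Table 3 in 2.1.4.2 for how each event is identified. The whole Table 3 entry for genital mycotic infection is "PTs in Appendix B". Appendix B lists eight PTs for it; the more general ones include "Genital infection fungal" and "Vulvovaginal mycotic infection". The SAP commits explicitly to listing investigator-reported EOSIs only in its paragraph on adjudicated events. For the others, the Listings paragraph promises EOSI listings where appropriate.

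**The concern.** The protocol collects the investigator's judgement that an event is a genital mycotic infection, and the SAP then counts the category without using it. Clinical diagnoses with no organism named are foreseeable. The protocol asks for urine culture when a urinary tract infection is suspected, but I found no organism test for suspected genital infection.

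Protocol 4.5 puts these infections among the programme's identified and potential risks and says the SGLT2 inhibitor class is associated with more genital infections. A category total that misses clinically diagnosed cases would understate the incidence in every arm, and the absolute excess over placebo with it.

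**Working it through.** The plan states no event rate or coding share for this EOSI, so there is no figure of its own to reproduce. The check is a reading of the counting rule, followed by an illustration on assumed inputs.

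**Step 1: what qualifies.** The eight PTs, sorted by the word that names the cause:
- candida or candidiasis (four): Balanitis candida, Genital candidiasis, Vulvovaginal candidiasis, Candida cervicitis
- fungal (three): Genital infection fungal, Urogenital infection fungal, Fungal balanitis
- mycotic (one): Vulvovaginal mycotic infection

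That is 8 of 8 naming a fungal cause and 0 of 8 organism-free.

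**Step 2: follow one event.** An investigator reports an event as this EOSI with the term balanitis and names no organism. If coding adds no organism, the PT matches none of the eight. Table 3 has no second route, so the patient is not in the EOSI row. An event coded to "Genitourinary tract infection" would count as a urinary tract infection, because that organism-free PT is on the UTI list only. A reported term that does say fungal can reach one of the general PTs, so the gap is confined to terms without an organism.

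**Step 3: compare other rows of Table 3.** Severe hypoglycemia is identified by an eCRF algorithm and an AE leading to amputation by an eCRF procedure page. Sustained eGFR decline and dialysis accept either an eCRF record or positive adjudication. Using investigator-entered data, alone or with an alternative route, is thus already an accepted pattern in this SAP.

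**Step 4: size, on assumed inputs.** Let u be the share of affected patients missed, equal in all arms.

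Counted risk = (1 - u) x true risk. Hence counted difference = (1 - u) x true difference, and counted ratio = true ratio.

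Planned arm sizes are from Protocol 11.1: 280 on 400 mg and 140 on placebo. The true risks and u are my assumptions.

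| True risk, 400 mg v placebo | u | Counted risk | Expected patients counted | Difference (points) | Ratio |
|---|---|---|---|---|---|
| 6% v 2% | 0 | 6.0% v 2.0% | 16.8 v 2.8 | 4.0 | 3.0 |
| | 0.10 | 5.4% v 1.8% | 15.1 v 2.5 | 3.6 | 3.0 |
| | 0.25 | 4.5% v 1.5% | 12.6 v 2.1 | 3.0 | 3.0 |
| | 0.40 | 3.6% v 1.2% | 10.1 v 1.7 | 2.4 | 3.0 |
| 10% v 2% | 0 | 10.0% v 2.0% | 28.0 v 2.8 | 8.0 | 5.0 |
| | 0.10 | 9.0% v 1.8% | 25.2 v 2.5 | 7.2 | 5.0 |
| | 0.25 | 7.5% v 1.5% | 21.0 v 2.1 | 6.0 | 5.0 |
| | 0.40 | 6.0% v 1.2% | 16.8 v 1.7 | 4.8 | 5.0 |

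If the share differed by arm, the ratio would be multiplied by (1 - u on active) / (1 - u on placebo). Nothing in the documents suggests in which direction.

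**The case against.** **The list fits the definition.** The EOSI is mycotic infection, and a fungus-specific list matches that. Counting events with no stated organism buys sensitivity at the price of specificity. Protocol 11.4.3.4 promises a count per EOSI without saying that it must come from the eCRF entry. This stands: a reader might infer that the SAP contradicts the protocol on the count, and it does not. It is a reason to show a second count and not to replace the first.

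**The event is still reported.** It stays in the all-AE listing with its reported term and, if treatment-emergent, in the TEAE tables. So a reader who infers that it disappears from the safety report would be wrong. The TEAE tables do not rebuild the category total, though: the events spread over several PT rows, and patients cannot be summed across rows.

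**Other EOSIs.** It is tempting to extend the point to every EOSI without adjudication. The documents do not support that. Severe hypoglycemia uses an eCRF algorithm; diarrhea and breast and prostate cancer use standardised MedDRA queries. The UTI and volume depletion lists contain broad terms, and no missed event can be shown for them, for pancreatitis or for venous thrombosis. Nor are the lists frozen, since a footnote updates search terms to the MedDRA version in force at database lock. That update would still not bring in investigator-reported events.

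**The comparison may be unaffected.** Safety is descriptive, and the comparative measure SAP 2.4.5 names is the relative risk, which equal proportional loss leaves alone. This stands for the ratio, but not for the incidence or the absolute difference.

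**The data field is not shown.** The CRF is not among the documents. Protocol 10.4.5 sends non-serious EOSIs through ordinary AE reporting, and Table 3 names no eCRF page for this category. This is a fair caution about feasibility.

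**Conclusion.** The point holds for one category. The genital mycotic infection count takes in only PTs that name a fungal cause, and an event reported by the investigator as this EOSI but coded without one is left out of it. Separately, the protocol's listing of investigator-reported EOSIs is carried into the SAP explicitly only for adjudicated events.

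The size is unknown. On the assumed inputs above, with 10-40% of affected patients missed equally in each arm, a 4.0-point difference is tabulated as 3.6-2.4 points and an 8.0-point difference as 7.2-4.8, with the ratios unchanged at 3.0 and 5.0. A reader might infer that the rule hides more in the active arms. That is so only in absolute numbers, because more patients are affected there; the proportion missed need not differ. Protocol 4.5 also does not say whether genital mycotic infection is an identified or a potential risk, so the case should not lean on the first label.

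**What to change.** 1. Keep the Appendix B count for genital mycotic infection. In SAP Table 3 and 2.4.5.2, add beside it the number and percentage of patients whose event was either reported by the investigator as this EOSI on the eCRF or matches an Appendix B PT. Show the components: listed PT, investigator report, and both.
2. State in SAP 2.4.5.2 that investigator-reported EOSIs without adjudication are listed, as Protocol 11.4.3.4 provides.
3. Confirm first that the eCRF records the EOSI category. If it does not, only the listing is feasible as it stands, and the SAP should say so.

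The cost is one extra table row with its components and one listing. The broader count is less specific for fungal infection and may look slightly less favourable, which is why the two belong side by side. If no organism-free events were reported and every investigator-reported event codes to a listed PT, the two counts agree and nothing is lost.
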